**8.5. Safety Assessments**

The investigator and any designees are responsible for detecting, documenting, and reporting events that meet the definition of an AE or SAE. The investigator and any designees remain responsible for following up AEs that are serious, considered related to the study treatment or the study, or that caused the subject to discontinue the study treatment or study.

**8.5.1. Safety definitions**

Please refer to Section [12.5](#) for safety definitions.

**8.5.2. Follow-up Clinic Visit(s)**

A follow-up clinic visit will be performed on Day 31 (-5/+14 days, Visit 2), Day 91 (-5 / +14 days, Visit 4) and Day 211 (-5 / +14 days, Visit 6).

The eDiary will be reviewed on Day 31 (Visit 2), Day 91 (Visit 4) and Day 211 (Visit 6).

Study-specific requirements are described in the SPM. For details on the eDiary see Section [12.5.9](#).

The subject and/or parent(s)/legal guardian(s) will be interviewed to determine if any unsolicited AEs occurred and if any concomitant medications or vaccines were taken/received in the time since the last clinic visit. The qualified healthcare professional reviewing these data will discuss the symptoms (if any) reported by the subject and will determine if any additional diagnoses and/or AEs are/were present. Adverse events reported by the subject and/or parent(s)/legal guardian(s) at this follow-up clinic visit must be recorded in the subject's source document and on an Adverse Events CRF, as specified in Section [8.5](#), and not written on the script used for the interview.

Perform a brief symptom-directed physical examination if necessary according to symptoms the subject has reported. This is a physical examination that will include an examination of organ systems that are relevant to the investigator based on review of the subject's reported adverse events, concomitant medication use. This assessment may include: measurement of vital signs, body temperature (preferably oral) and a check of general appearance. The physical assessment must be performed by the investigator or designee of the investigator, who is qualified to perform a physical assessment in

**CONFIDENTIAL**205416 [MENB REC 2ND GEN-038 (V72\_72)]  
Protocol Amendment 4 Final

accordance with their institutional policy. Clinically significant abnormalities should be reported as an AE in the CRF.

Blood sampling will be done as described in Section 8.4.2.1.

The site should schedule the next study visit/ study activity safety call with the subject and/or parent(s)/legal guardian(s) at each visit. The subject and/or parent(s)/LAR(s) will be reminded to contact the site if there are any questions and to contact the site immediately (or as soon as the subject is medically stable) if the subject has a medical condition that leads to a hospitalisation or an emergency room visit.

**8.5.3. Safety Follow-up Calls**

Safety follow-up phone calls are made on Day 15 (T1), Day 75 (T2), Day 121 (T3), Day 195 (T4), Day 241 (T5), Day 301 (T6), and Day 361 (T7). Safety follow-up calls are made to the subject by a qualified healthcare professional designated on the site log. These calls will follow a script which will facilitate the collection of relevant safety information. The subject and/or parent(s)/legal guardian(s) will be interviewed at Day 15 (SFU 1; T1), Day 75 (SFU 2; T2) and Day 195 (SFU 4; T4) according to the script, and information relating to any unsolicited AEs will be collected.

At all safety follow-up phone calls (T1 to T7) information relating to SAEs, AESIs, medically attended AEs and AEs leading to withdrawal will be collected. At all Safety Follow-up Calls concomitant medications associated with the AE and concomitant vaccinations have to be collected. All safety information described by the subject must be written down in a designated location within the source document. If this script is used as a source document, ensure that it meets the definition of a source document as per ICH GCP and/or local requirements.

The site should schedule the next study activity clinic (visit or safety call) with the subject and/or parent(s)/LAR(s).

The subject and/or parent(s)/legal guardian(s) will be reminded to contact the site if there are any questions and to contact the site immediately (or as soon as the subject is medically stable) if the subject has a medical condition that leads to a hospitalisation or an emergency room visit.

**CONFIDENTIAL**205416 [MENB REC 2ND GEN-038 (V72\_72)]  
Protocol Amendment 4 Final**8.5.4. Time period and frequency for collecting AE and serious adverse event (SAE) information**

An overview of the protocol-required reporting periods for AEs, SAEs, AESIs and pregnancies is given in [Table 14](#). Refer to the Section [12.5.9.2](#) for details on the time period for recording safety information.

**Table 14 Reporting periods for collecting safety information**

Event	On V1*	V1 D1***	D7	V2 D31	V3 D61	D67	V4 D91	V5 D181	D 187	V6 D 211	D241	D301	Study Conclusion D 361
Solicited local and systemic AEs													
Unsolicited AEs													
AEs leading to withdrawal from the study													
Medically attended AEs**													
SAEs													
SAEs related to study participation or concurrent GSK medication/vaccine													

**CONFIDENTIAL**205416 [MENB REC 2ND GEN-038 (V72\_72)]  
Protocol Amendment 4 Final

Event	On V1*	V1 D1***	D7	V2 D31	V3 D61	D67	V4 D91	V5 D181	D 187	V6 D 211	D241	D301	Study Conclusion D 361
AESIs		[REDACTED]											
Pregnancies		[REDACTED]											

.; V: Visit; D: Day, M: Month; T, Telephone call; COVID-19, Coronavirus Disease 2019

\* i.e. consent obtained

\*\* Including COVID-19 infection related AEs.

\*\*\* Except SAEs related to study participation or concurrent GSK medication/vaccine, all other safety data will be collected starting from Visit 1 after vaccine administration.

All SAEs will be recorded and reported via Expedited AE Reporting Form to the sponsor or designee immediately and under no circumstance should this exceed 24 hours after the investigator became aware of it, as indicated in Section 12.5. The investigator will submit any updated SAE/AESI data to the sponsor within 24 hours of it being available.

A post-study AE/SAE is defined as any event that occurs outside of the AE/SAE reporting period defined in Table 14.

Investigators are not obligated to actively seek AEs or SAEs in former study subjects. However, if the investigator learns of any SAE, including a death, at any time after a subject has been discharged from the study, and he/she considers the event to be reasonably related to the study vaccine(s)/product(s), the investigator will promptly notify the Study Contact for Reporting SAEs.

**CONFIDENTIAL**205416 [MENB REC 2ND GEN-038 (V72\_72)]  
Protocol Amendment 4 Final**8.5.5. Method of detecting AEs and SAEs**

The method of recording, evaluating, and assessing intensity, causality and outcome of AEs and SAEs and the procedures for completing and transmitting SAE reports are provided in Section 12.5.9.

Care will be taken not to introduce bias when detecting AE and/or SAE. Open-ended and non-leading verbal questioning of the subjects/subjects' parent(s)/LAR(s) is the preferred method to inquire about AE occurrence.

**8.5.6. Reporting of serious adverse events, pregnancies, and other events**

(Amended 9 May 2021)

**Table 15 Timeframes for submitting serious adverse event, pregnancy and other events reports to GSK**

Type of Event	Initial Reports		Follow-up of Relevant Information on a Previous Report	
	Timeframe	Documents	Timeframe	Documents
SAEs	24 hours* ‡	electronic Expedited Adverse Events Report	24 hours*	electronic Expedited Adverse Events Report
Pregnancies	24 hours*	electronic pregnancy report	24 hours*	electronic pregnancy report
AESIs	24 hours** ‡	electronic Expedited Adverse Events Report	24 hours*	electronic Expedited Adverse Events Report

\* Timeframe allowed after receipt or awareness of the information.

\*\*Timeframe allowed once the investigator determines that the event meets the protocol definition of an AESI

‡ The investigator will be required to confirm review of the SAE/AESI causality by ticking the 'reviewed' box in the electronic Expedited Adverse Events Report within 72 hours of submission of the SAE/AESI

**8.5.6.1. Contact information for reporting of serious adverse events, AESIs and pregnancies****Table 16 Contact information for reporting of serious adverse events, AESIs and pregnancies**

Study contact for questions regarding SAEs, AESIs and pregnancies
Refer to the local study contact information document
Back-up Study Contact for Reporting SAEs, AESIs and pregnancies
24/24 hour and 7/7 day availability:
GSK Clinical Safety & Pharmacovigilance
Outside US & Canada sites:
[contact] or [contact]
Email address: [contact]
US sites only:
[contact]
Canadian sites only:
[contact]

**CONFIDENTIAL**205416 [MENB REC 2ND GEN-038 (V72\_72)]  
Protocol Amendment 4 Final**8.5.6.2. Regulatory reporting requirements for SAEs**

Prompt notification of an SAE by the investigator to the sponsor is essential for meeting legal obligations and ethical responsibilities for the safety of subjects and the safety of a study treatment under clinical investigation.

The sponsor has a legal responsibility to notify both the local regulatory authority and other regulatory agencies about the safety of a study treatment under clinical investigation. The sponsor will comply with country-specific regulatory requirements relating to safety reporting to the regulatory authority, Institutional Review Boards (IRB)/Independent Ethics Committees (IEC), and investigators.

Investigator safety reports must be prepared for suspected unexpected serious adverse reactions (SUSAR) according to local regulatory requirements and sponsor policy and forwarded to investigators as necessary.

An investigator who receives an investigator safety report describing a SAE or other specific safety information (e.g. summary or listing of SAEs) from the sponsor will review and then file it along with the Investigator's Brochure and will notify the IRB/IEC, if appropriate according to local requirements.

**8.5.7. Follow-up of AEs and SAEs**

After the initial AE/SAE report, the investigator is required to proactively follow each subject at subsequent visits/contacts. All SAE and non-serious AESIs (Refer Section 12.5.6 for definition), will be followed until the event is resolved, stabilised, otherwise explained, or the subject is lost to follow-up. Further information on follow-up procedures is given in Section 12.5.12.4.

**8.5.8. Treatment of adverse events**

Treatment of any AE is at the sole discretion of the investigator and according to current good medical practice. Any medication administered for the treatment of a SAE/ AESI should be recorded in Expedited Adverse Event Report of the subject's eCRF (refer to Section 7.5).

**8.5.9. Subject card**

Study subjects/subjects' parent(s)/LAR(s) must be provided with the address and telephone number of the main contact for information about the clinical study.

The investigator (or designate) must therefore provide a "subject card" to each subject/subject's parent(s)/LAR(s). In an emergency situation, this card serves to inform the responsible attending physician that the subject is in a clinical study and that relevant information may be obtained by contacting the investigator.

Subjects/subjects' parent(s)/LAR(s) must be instructed to keep subject cards in their possession at all times during the study duration.

**CONFIDENTIAL**205416 [MENB REC 2ND GEN-038 (V72\_72)]  
Protocol Amendment 4 Final**8.5.10. Medical device deficiencies**

(Amended 9 May 2021)

*The study interventions (MenABCWY and Bexsero) are combination products constituted of a device and biologic product (e.g., pre-filled syringes). Refer to [Glossary of terms](#) for the definition of a combination product and a medical device deficiency.*

**8.5.10.1. Detection, follow-up and prompt reporting of medical device deficiency**

*The investigator is responsible for the detection, documentation and prompt reporting of any medical device deficiency occurring during the study to GSK. This applies to any medical device provided for the conduct of the study.*

*Device deficiencies will be reported to GSK within 24 hours after the investigator determines that the event meets the protocol definition of a device deficiency. Refer to [Section 12.8](#) for definitions and details on recording and reporting of these events.*

*The investigator will ensure that follow-up includes any additional investigations to elucidate the nature and/or related of the device deficiency to the incident. Follow-up applies to all participants, including those who discontinue study intervention or the study.*

*New or updated information will be recorded on the originally completed form with all changes signed and dated by the investigator and reported to GSK within 24 hours.*

**8.5.10.2. Regulatory reporting of medical device deficiency when used as combination product**

*The investigator will promptly report all device deficiencies occurring with any medical device provided for use in the study to GSK. GSK has a legal responsibility to notify appropriate regulatory authorities and other entities about safety information linked to medical devices being used in clinical studies. Refer to [Section 12.8.2](#) for details of reporting.*

*The investigator, or responsible person according to local requirements (e.g. the head of the medical institution), will comply with the applicable local regulatory requirements relating to the reporting of device deficiencies to the IRB/IEC.*

**8.6. Holding rules and safety monitoring**

There are no predetermined stopping rules other than circumstances for which subjects may not be eligible for additional study vaccinations or may be withdrawn from the study according to the best interests of the subject.

**8.7. Biomarkers and pharmacogenomics**

Biomarkers and pharmacogenomics are not evaluated in this study.

**CONFIDENTIAL**205416 [MENB REC 2ND GEN-038 (V72\_72)]  
Protocol Amendment 4 Final**8.8. Study Termination Visit/ Study Conclusion**

The study termination call will occur on Day 361. The termination visit will be a phone call (also in case of early termination of the study).

The date of termination is the date of the last contact (telephone call) in which the subject's health status was assessed or, in cases where the subject does not agree to any further safety follow-up, it is the date consent is withdrawn. This date should be recorded on the termination eCRF page. For visit procedures to be performed for a subject whose planned study participation ends prematurely, please see Section 8.8.1.

During the phone call at the end of the study (Day 361), the following procedures will be performed: interview of subject and/or parent(s)/legal guardian(s) to collect SAEs, AESIs, medically attended AEs, pregnancies and/or concomitant medications/vaccinations.

The site will review with the subject and/or parent(s)/legal guardian(s) the plan of when information relating to the subject's participation in the study may be available (e.g., study results, treatment assignments). It will also be discussed how information relating to the subject's participation in the study will be shared with the subject's healthcare provider, if the subject and/or parent(s)/legal guardian(s) chooses to share this information.

The site will complete the termination eCRF page and this will mark the completion of the subject's participation in the study.

**8.8.1. Early Termination Visit**

When a subject is withdrawn from treatment or withdraws from the study, the investigator will perform the procedures listed below. The reason(s) for the early termination will be included in the subject's source documentation. If the Early Termination Visit is a telephone call, collect as much information as possible. Early Termination Visits include subjects who were randomised but not treated.

At the clinic visit or during the telephone call, the following procedures will be performed:

- review of Subject eDiary (if applicable)
- interview of subject and/or parent(s)/legal guardian(s) to collect all AEs if termination occurs within 30 days after vaccination. If the termination occurs more than 30 days after the vaccination, all AEs within 30 days after vaccination and medically attended AEs, AEs leading to withdrawal, SAEs, pregnancy, AESIs beyond the 30 days after vaccination have to be collected.
- interview of subject and/or parent(s)/legal guardian(s) to collect concomitant medications administered to treat adverse events collected in the study,
- blood sampling (if withdrawal occurs at or prior to Visit 4 (Day 91) or Visit 6 (Day 211)) (if applicable)

**CONFIDENTIAL**205416 [MENB REC 2ND GEN-038 (V72\_72)]  
Protocol Amendment 4 Final

The site will review with the subject and/or parent(s)/legal guardian(s) the plan of when information relating to the subject's participation in the study may be available (e.g., study results, treatment assignments). It will also be discussed how information relating to the subject's participation in the study will be shared with the subject's healthcare provider, if the subject and/or parent(s)/legal guardian(s) chooses to share this information.

The site will complete the termination eCRF page and this will mark the completion of the subject's participation in the study.

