## **7. TREATMENTS**

Study treatment is defined as a set of investigational product(s) or marketed product(s) or placebo intended to be administered to a subject.

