Any subject who becomes pregnant during the study, despite the protocol requirement for adequate contraception, will not receive further vaccination but should be encouraged to continue participating in the study for safety follow-up. The site must complete a Pregnancy Report eCRF (initial report) as soon as possible after learning of pregnancy occurrence (Refer to Section 12.5.9). If the subject withdraws from the study for any of the above categories except death, the site will obtain permission from the subject to continue to remain in contact with her until the outcome of the pregnancy is known, even if the outcome is not known until after the subject reaches the end of follow-up period.

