**9.1. Discontinuation of study vaccine(s)/product(s)**

A 'withdrawal' from the study vaccine(s)/product(s) refers to any subject who does not receive the complete treatment, i.e. when no further planned dose is administered from the date of withdrawal. A subject withdrawn from the study vaccine(s)/product(s) may continue further study procedures (safety or immunogenicity) if planned in the study protocol, as deemed appropriate by the investigator.

Primary reason relative to premature discontinuation of the study vaccine(s)/product(s) will be documented on the Vaccine Administration screen of the eCRF. The investigator will document whether the decision to discontinue further vaccination/treatment was made by the subject himself/herself, by the subject's parent(s)/LAR(s), or by the investigator, as well as which of the following possible reasons was responsible for withdrawal:

- Adverse event requiring expedited reporting
- Unsolicited non-serious adverse event (specify)
- Solicited adverse event
- Not willing to be vaccinated
- Other (specify).

**CONFIDENTIAL**205416 [MENB REC 2ND GEN-038 (V72\_72)]  
Protocol Amendment 4 Final**9.2. Lost to follow-up**

A subject will be considered lost to follow-up if he or she repeatedly fails to return for scheduled visits and is unable to be contacted by the study site.

The following actions must be taken if a subject fails to return to the clinic for a required study visit:

- The site must attempt to contact the subject and reschedule the missed visit as soon as possible and counsel the subject on the importance of maintaining the assigned visit schedule and ascertain whether or not the subject wishes to and/or should continue in the study.
- Before a subject is deemed lost to follow-up, the investigator or designee must make every effort to regain contact with the subject (where possible, 3 telephone calls and, if necessary, a certified letter to the subject's last known mailing address or local equivalent methods). These contact attempts should be documented in the subject's medical record.
- Should the subject continue to be unreachable, he/she will be considered to have withdrawn from the study with a primary reason of lost to follow-up. The termination date for the subject to be captured on the Study Termination eCRF page is the date of the last successful contact (clinic visit or telephone) with the subject.

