**12.6.3. Collection of pregnancy information****12.6.3.1. Female Subjects who become pregnant****(Amended 9 May 2021)**

- Investigator will collect pregnancy information on any female subject, who becomes pregnant while participating in this study.
- Information will be recorded on the appropriate form and submitted to GSK within **24 hours** of learning of a subject's pregnancy.
- Subject will be followed to determine the outcome of the pregnancy. The investigator will collect follow-up information on subject and neonate, which will be forwarded to GSK. Generally, follow-up will not be required for longer than 6 to 8 weeks beyond the estimated delivery date.
- Any termination of pregnancy will be reported, regardless of fetal status (presence or absence of anomalies) or indication for procedure.

**CONFIDENTIAL**205416 [MENB REC 2ND GEN-038 (V72\_72)]  
Protocol Amendment 4 Final

- While pregnancy itself is not considered to be an AE or SAE, any pregnancy complication or elective termination of a pregnancy will be reported as an AE or SAE.
- A spontaneous abortion is always considered to be an SAE and will be reported as such.
- Any SAE occurring as a result of a post-study pregnancy which is considered reasonably related to the study treatment by the investigator, will be reported to GSK as described in Section 12.5.10. While the investigator is not obligated to actively seek this information in former study subjects, he or she may learn of an SAE through spontaneous reporting.

Please see section 12.5.9 , 12.5.10 and 12.5.12.4.3 for further information on detection, recording, reporting and follow-up of pregnancies.

Any female subject who becomes pregnant while participating will discontinue study treatment.

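### Section 8.8.1 requires a participation-ending Early Termination Visit for a subject who only stops vaccination, although Sections 7.7, 9, 9.1 and 12.5.8.1 let that subject stay in the study

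*Protocol*

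**What the plan says.** Section 8.8.1 (Early Termination Visit) gives two alternative triggers: "When a subject is withdrawn from treatment or withdraws from the study, the investigator will perform the procedures listed below". After the listed procedures, it says "The site will complete the termination eCRF page and this will mark the completion of" the subject's participation. A separate sentence in the same section covers subjects who were randomised but never treated.

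Other sections set different rules for a subject who stops vaccination but has not left the study:

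- Section 7.7 (contraindications) says these subjects should be encouraged to go on with other study procedures, at the investigator's discretion.
- Section 9, in its paragraph on pregnancy, says the subject "will not receive further vaccination but should be encouraged to continue participating in the study for safety follow-up".
- Section 9.1 says: "A subject withdrawn from the study vaccine(s)/product(s) may continue further study procedures (safety or immunogenicity) if planned in the study protocol", as the investigator judges appropriate. It also fixes where the stop is recorded: "Primary reason relative to premature discontinuation of the study vaccine(s)/product(s) will be documented on the Vaccine Administration screen of the eCRF".
- Section 12.5.8.1 lets pregnant or lactating subjects continue other procedures, at the investigator's discretion.
- Section 12.5.9.2 runs collection of SAEs, AESIs and pregnancies to Day 361 (call T7) and does not shorten it when vaccination stops.

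**The concern.** The same subject falls under two incompatible instructions. Section 8.8.1 ends participation; the other sections let it go on. A site cannot do both.

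What is at stake is safety follow-up. The percentages of subjects with SAEs, AEs leading to withdrawal, AESIs and medically attended AEs from Month 0 to Month 12 are a primary safety endpoint (Section 4, Table 6). Once a subject has been discharged, Section 8.5.4 no longer obliges the investigator to look for new events. Section 9.1 lists five reasons for stopping vaccine. Three are adverse events of some kind; the other two are "Not willing to be vaccinated" and an open category. The subjects exposed to early closure therefore include some who stopped because of a possible reaction.

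**Working it through.** The plan gives no figure on this point, so there is none to reproduce. The check is first textual, then a count of days and calls.

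**Does the trigger reach a vaccine-only stop?** Section 7 says: "Study treatment is defined as a set of investigational product(s) or marketed product(s) or placebo intended to be administered to a subject". Section 12.6.3.1 says: "Any female subject who becomes pregnant while participating will discontinue study treatment". Treatment in this protocol therefore means the injections, and a pregnant subject who stays for safety follow-up has been taken off treatment. Section 8.5 (AEs that caused a stop of treatment or of study) and Table 3 (vaccine or study withdrawal) also keep the two kinds of stop apart. So the first limb of the trigger in 8.8.1 cannot be read as another name for leaving the study.

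**Is the first limb needed for anyone?** Subjects randomised but not treated have their own sentence in 8.8.1, and Section 7.2.2.2.1 already calls that an early termination. Subjects who stop vaccine and then leave are caught by the second limb. The only people whom the first limb adds are those who stop vaccine and stay.

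**Do the records agree?** Section 9.1 puts a vaccine stop on the Vaccine Administration screen, whereas 8.8.1 would put the same subject on the termination page. Section 9 defines withdrawal from the study separately, as the point after which there are no further procedures, follow-up or information.

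**How much follow-up could one subject lose?** Section 8.5.3 schedules seven calls: T1 Day 15, T2 Day 75, T3 Day 121, T4 Day 195, T5 Day 241, T6 Day 301 and T7 Day 361. Days lost = 361 minus the closing day; calls lost = calls scheduled after that day.

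| Closed at | Days lost | Calls lost |
|---|---|---|
| Day 61 (Visit 3) | 361 − 61 = 300 | T2 to T7 = 6 of 7 |
| Day 181 (Visit 5) | 361 − 181 = 180 | T4 to T7 = 4 of 7 |
| Day 211 (Visit 6) | 361 − 211 = 150 | T5 to T7 = 3 of 7 |

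The last row includes a subject who declines only the Day 211 injection. Section 5.2 ties that injection to no objective, but Table 9 counts it among the planned doses, so under Section 9.1 the course is incomplete.

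These are nominal ceilings per subject. Blood draws are left out, because continuing them is discretionary and, for pregnancy, Section 9 encourages only safety follow-up.

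**The case against.** The strongest reply is that 8.8.1 has a narrower scope when read in place. It sits under the section on study termination, and its title and second sentence speak of early termination. Section 8.8 sends sites there when participation ends prematurely, and Table 3, footnote 8, does so for subjects who terminate the study early. A consistent reading is then available: a vaccine stopper who continues follows 9.1, and one who does not continue gets the 8.8.1 visit. Section 9.1 is also the dedicated section on stopping vaccine, and Section 12.5.9.2 keeps SAE, AESI and pregnancy collection open to Day 361 without regard to vaccination status.

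Much of this stands. It settles the intent, and it means that a site applying 7.7, 9, 9.1 or 12.5.9.2 would keep the subject in follow-up. It does not cure the operative sentence, which is mandatory, makes a treatment stop sufficient on its own, and has no exception. Section 12.5.9.2 adds another passage that the sentence conflicts with.

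A reader might infer that everyone who stops vaccine drops out of safety follow-up and that the primary safety endpoint is therefore biased. The documents do not support that. They do not say how many subjects would stop vaccine only, or how sites would read 8.8.1. The 25% drop-out assumed in Section 10.1 is not split between vaccine stops and study withdrawals. Nor is all information lost: 8.8.1 itself collects AEs up to termination, Section 12.5.12.4.2 continues to follow known SAEs, AESIs and AEs that led to withdrawal, and Section 12.5.12.4.3 follows pregnancies to outcome.

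**Conclusion.** Section 8.8.1 is wrong as written and needs a minor correction. Its first trigger ends participation for subjects whom 7.7 and 9 (pregnancy) encourage to continue and 9.1 and 12.5.8.1 permit to continue, and it cuts across the Day 361 collection period in 12.5.9.2. The cause is probably a drafting slip; the cross-references do not support reading it as a deliberate rule.

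The consequence is early loss of active collection of new SAEs, AESIs and medically attended AEs, up to the per-subject ceilings tabulated above. Two conditions must both hold: the site follows 8.8.1 over the more specific sections, and the subject would otherwise have stayed. Confidence in the wording conflict is high. The practical effect is conditional, and no study-wide size can be given. No effect on the effectiveness or immunogenicity objectives is claimed.

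**What to change.** In 8.8.1, replace the two-part trigger so that the procedures apply when a subject *withdraws, or is withdrawn, from the study*. Add one sentence: *Subjects who stop vaccination only are handled under Sections 7.7, 9 (pregnancy), 9.1 and 12.5.8.1; the termination eCRF page is completed only when study participation ends.*

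Keep the sentence on subjects randomised but not treated. Do not add encouragement to continue beyond what 7.7 and 9 already contain: 9.1 only permits it, for safety and immunogenicity procedures alike, as the investigator judges appropriate, and that discretion should stay.

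The cost is one sentence changed and one added at the next amendment. The criteria for stopping vaccination are unchanged, and any further calls or blood draws fall on subjects whom the protocol already allows to continue.
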